## 1.0 TRIAL SUMMARY

Abbreviated Title	Phase II Study of pembrolizumab in Subjects with Human Papillomavirus-associated Recurrent Respiratory Papillomatosis
Trial Phase	II
Clinical Indication	The treatment of subjects with recurrent respiratory papillomatosis with extensive laryngeal, tracheal and/or pulmonary involvement
Trial Type	Interventional
Type of control	No treatment control
Route of administration	Intravenous
Trial Blinding	Unblinded Open-label
Treatment Groups	Pembrolizumab 200 mg every 3 weeks
Number of trial subjects	Approximately 22 subjects will be enrolled
Estimated enrollment period	Approximately 18-24 months
Estimated duration of trial	It is estimated that the trial will require approximately 60 months from the time the first subject signs the informed consent until the last subject's last visit.
Duration of Participation	Each subject will participate in the trial from the time the subject signs the Informed Consent Form (ICF) through the final protocol-specified contact. After a screening phase of 28 days, eligible subjects will register then to receive treatment on Day 1 of each 3-week dosing cycle. Treatment with pembrolizumab will continue until documented confirmed disease progression, unacceptable adverse event(s), intercurrent illness that prevents further administration of treatment, investigator's decision to withdraw the subject, subject withdraws consent, pregnancy of the subject, noncompliance with trial treatment or procedure requirements, completion of 24 months of treatment with pembrolizumab, or administrative reasons. Subjects who attain a complete response may consider stopping trial treatment if they meet criteria for holding therapy. These subjects will be eligible for re-treatment after experiencing disease progression at the discretion of the investigator if they meet the criteria for re-treatment and the trial is ongoing. After the end of treatment, each subject will be followed for 30 days for adverse event monitoring (serious adverse events will be collected for 90 days after the end of treatment). Subjects who discontinue protocol treatment for reasons other than disease progression will have post-treatment follow-up for disease status until first disease progression, initiating a non-study cancer treatment, withdrawing consent, becoming lost to follow-up, death, or 36 months from study registration whichever occurs first. Following first disease progression, subjects will be followed by telephone for overall survival until death, withdrawal of consent, or 36 months from study registration whichever occurs first.

---

CONFIDENTIAL

*This document is confidential. Do not disclose or use unless authorized.*

## 2.0 TRIAL DESIGN

### 2.1 Trial design

This is a non-randomized phase II trial in male and female subjects diagnosed with recurrent respiratory papillomatosis (RRP) with extensive laryngeal, tracheal and/or pulmonary involvement. Approximately 22 subjects will be enrolled in this trial to examine the safety and efficacy in this subject population who would be administered up to 200 mg of pembrolizumab every 3 weeks. Subjects will be evaluated every 3 weeks (21 days  $\pm$  3 days) in the clinic with a video-recorded transnasal flexible laryngoscopy and tracheoscopy examination to assess clinical response on treatment (**Appendix A**) as well as evaluated every 24 weeks (169 days  $\pm$  14 days) with CT scans to assess response per volumetric analysis. For those patients with pulmonary lesions measurable by RECIST 1.1, CT scans of the chest will be obtained every 12 weeks (84 days  $\pm$  7 days) to assess response per RECIST 1.1 criteria. In addition, patients will complete quality of life questionnaires to assess preference of pembrolizumab as compared to standard of care treatment, which is surgery, for this patient population (**Appendix F**).

As part of the natural course of this disease, patients undergo operative procedures for repeated debridement of papillomata within their upper aerodigestive tract in order to improve their breathing and/or voice quality. Prior to starting pembrolizumab, subjects will undergo a comprehensive laryngoscopy and tracheobronchoscopy to map and score their disease burden in the upper aerodigestive tract and a pre-treatment biopsy would be obtained at that time. Subsequently, at a minimum of every 12 weeks (84 days  $\pm$  14 days), subjects will be taken to the operating room for a comprehensive laryngoscopy and tracheobronchoscopy and debridement of any papillomatous lesions which obstructs the caliber of their airway by more than 50% and/or other lesions at the discretion of the surgeon. Some patients will require more frequent visits to the operating room depending on their disease burden and associated clinical symptoms. Biopsies will be obtained during all operative visits.

Adverse events will be monitored throughout the trial and graded in severity according to the guidelines outlined in the NCI Common Terminology Criteria for Adverse Events (CTCAE) version 4.0. Treatment with pembrolizumab will continue until documented disease progression, unacceptable adverse event(s), intercurrent illness that prevents further administration of treatment, investigator's decision to withdraw the subject, subject withdraws consent, pregnancy of the subject, noncompliance with trial treatment or procedure requirements, completion of 24 months of treatment with pembrolizumab, or administrative reasons. Subjects who attain an investigator-determined confirmed complete response (CR) may consider stopping trial treatment after receiving at least 24 weeks of treatment. Subjects who discontinue after at least 24 months of therapy for reasons other than disease progression or intolerance or who discontinue after attaining a CR may be eligible for up to one year of re-treatment after they have experienced clinical and/or radiographic disease progression. The decision to retreat will be at the discretion of the investigator if no additional systemic immunotherapeutic treatment was administered since the last dose of pembrolizumab, the subject still meets the safety parameters listed in the Inclusion/Exclusion criteria and the trial remains open.

---

CONFIDENTIAL

*This document is confidential. Do not disclose or use unless authorized.*

After the end of treatment, each subject will be followed for 30 days for adverse event monitoring (serious adverse events will be collected for 90 days after the end of treatment). Subjects who discontinue treatment for reasons other than first disease progression will have post-treatment follow-up for disease status until disease progression, initiating a non-study systemic chemotherapeutic treatment, withdrawing consent, becoming lost to follow-up, death, or 36 months post study registration whichever occurs first. Following first disease progression, subjects will be followed by telephone contact for overall survival until death, withdrawal of consent or 36 months post study registration, whichever comes first. The study will be stopped if greater than 30% of patients discontinue pembrolizumab due to an adverse event or for any patient death related to toxicity.

The goal of this study is to evaluate the efficacy of pembrolizumab in this patient population to support treatment with systemic immunotherapy which could minimize and/or eliminate the need for multiple surgical procedures over the patient's lifetime. The primary objectives of the trial are to determine the anti-tumor activity, safety, and tolerability of pembrolizumab treatment in male and female subjects diagnosed with RRP. Secondary objectives include evaluating the relationship between candidate efficacy/resistance biomarkers and anti-tumor activity and response duration of pembrolizumab. An exploratory objective is to assess the quality of life of RRP patients with pembrolizumab. Established quality of life is lacking in this patient population and, in a separate study, we are establishing baseline quality of life parameters of RRP patients being treated with standard of care, which is repeated surgeries.

[figure not shown]
The study will be conducted in conformance with Good Clinical Practices.

Specific procedures to be performed during the trial, as well as their prescribed times and associated visit windows, are outlined in the Trial Flow Chart – Section 9.0. Details of each procedure are provided in Section 10.0 – Trial Procedures.

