### 7.1.2 Timing of Dose Administration

Trial treatment should be administered on Day 1 of each cycle after all procedures/assessments have been completed as detailed on the Trial Flow Chart (Section 9.0). Trial treatment may be administered up to 3 days before or after the scheduled Day 1 of each cycle due to administrative or other reasons.

All trial treatments will typically be administered on an outpatient basis.

Pembrolizumab up to 200 mg will be administered as a 30 minute IV infusion every 3 weeks. Sites should make every effort to target infusion timing to be as close to 30 minutes as possible. However, given the variability of infusion pumps from site to site, a window of -5 minutes and +10 minutes is permitted (i.e., infusion time is 30 minutes: -5 min/+10 min). Pembrolizumab will be administered after the operative endoscopy. If the patient is found to have progressive disease by endoscopic evaluation, the patient will continue to receive pembrolizumab until the next in-office clinical examination in 3 weeks which confirms progressive disease of the target lesion.

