T3, FT4 and TSH 		X 			X 						X 			
Efficacy Measurements														
Radiographic Tumor Imaging 		X								X 	X 		X 	X 
Clinical Imaging: Video-recording of flexible fiberoptic laryngoscopy, tracheoscopy  and/or bronchoscopy examination 		X 	X	X	X	X	X	X	X	X 	X	X	X 	
Tumor Biopsies/Archival Tissue Collection/Correlative Studies Blood														

*CONFIDENTIAL*

*This document is confidential. Do not disclose or use unless authorized.*

Trial Period:	Screening Phase		Treatment Cycles								End of Treatment (early or at 24 months)	Post-Treatment		
			To be repeated beyond 8 cycles											
Treatment Cycle/Title:	Main Study Screening (Visit 1)	1	2	3	4	5	6	7	8	Discon	Safety Follow-up	Follow Up Visits 	Survival Follow-Up	
Scheduling Window (Days)  :		-28 to -1		± 3	± 3	± 3	± 3	± 3	± 3	At time of Discon	30 days post discon ± 2 weeks	Every 8 weeks post discon ± 2 weeks	Every 24 weeks ± 2 weeks	
Archival or Newly Obtained Tissue Collection		X				X 				X 	X 			
HPV testing		X												
Correlative Studies Blood Collection		X				X				X	X 			
Quality of Life Questionnaires 		X				X				X	X 			

*CONFIDENTIAL*

*This document is confidential. Do not disclose or use unless authorized.*

Trial Period:	Screening Phase		Treatment Cycles								End of Treatment (early or at 24 months)	Post-Treatment		
							To be repeated beyond 8 cycles							
Treatment Cycle/Title:	Main Study Screening (Visit 1)	1	2	3	4	5	6	7	8	Discon	Safety Follow-up	Follow Up Visits 	Survival Follow-Up	
										At time of Discon	30 days post discon ± 2 weeks	Every 8 weeks post discon ± 2 weeks	Every 24 weeks ± 2 weeks	
Scheduling Window (Days):		-28 to -1	± 3	± 3	± 3	± 3	± 3	± 3	± 3					

In general, the window for each visit is +/- 3 days unless otherwise noted. For patients who have to travel >50 miles for treatment, there will be a window of +/- 7 days for each visit.

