 In subjects who discontinue study therapy without confirmed disease progression, a radiological and/or clinical imaging should be performed at the time of treatment discontinuation (i.e. date of discontinuation +/- 4 week window). If a previous scan was obtained within 4 weeks prior to the date of discontinuation, then a scan at treatment discontinuation is not mandatory.															
 In subjects who discontinue study therapy (early or at 24 months) without documented disease progression, every effort will be made to continue monitoring their disease status by radiologic imaging every 6 months (+/- 2 weeks) until: 1) documented disease progression; 2) death; or 3) 36 months post study registration, whichever occurs first.															
 Unresolved labs that are drug related AEs should be followed until resolution. Labs do not need to be repeated after the end of treatment if labs are within															

CONFIDENTIAL

*This document is confidential. Do not disclose or use unless authorized.*

Trial Period:	Screening Phase		Treatment Cycles								End of Treatment (early or at 24 months)	Post-Treatment		
			To be repeated beyond 8 cycles											
Treatment Cycle/Title:	Main Study Screening (Visit 1)	1	2	3	4	5	6	7	8	Discon	Safety Follow-up	Follow Up Visits 	Survival Follow-Up	
Scheduling Window (Days)  :		-28 to -1	$\pm 3$	$\pm 3$	$\pm 3$	$\pm 3$	$\pm 3$	$\pm 3$	$\pm 3$	At time of Discon	30 days post discon $\pm 2$ weeks	Every 8 weeks post discon $\pm 2$ weeks	Every 24 weeks $\pm 2$ weeks	

normal range.

Tumor biopsy will be obtained only if there are lesions present.

Tumor biopsy, blood for correlative studies for clinically stable subjects, and quality of life questionnaires should be obtained at treatment discontinuation.

Survival status should be obtained at each clinic visit and/or each tumor assessment. Following first disease progression, subjects will be followed by telephone for overall survival until death, withdrawal of consent, or 36 months from study registration, whichever occurs first.

Endoscopic evaluations at baseline should be done within 6 weeks prior to enrollment into the study.

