Clinical imaging assessed by laryngoscopy and tracheoscopy will be performed every 3 weeks (21 days $\pm$  3 days). In addition, a comprehensive laryngoscopy, tracheoscopy, and bronchoscopy will be performed every 4 cycles in the operating room.

VHI-10 questionnaire is required only for subjects enrolled after IRB approval and/or activation of Protocol AM 10

After 1 year, the clinical assessment will be reduced to 24 weeks for 12 months only.

*CONFIDENTIAL*

*This document is confidential. Do not disclose or use unless authorized.*

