### **10.1.2.3 Directed Physical Exam**

For cycles that do not require a full physical exam per the Trial Flow Chart, the treating investigator or qualified designee will perform a directed physical exam as clinically indicated prior to trial treatment administration. Patients will undergo a video-recorded transnasal flexible fiberoptic laryngoscopy and tracheoscopy examination within +/- 24 hours that they receive each dose of pembrolizumab. The treating surgeon will complete the Severity Scoring Sheets (found in Section 18.0A Surgical Scoring sheets) at each session and document procedure findings.

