#### **10.1.5.2 Treatment Period**

On-study visits will occur on day 1 of each cycle of Pembrolizumab and will include the following at every visit:

1. Directed physical examination with flexible fiberoptic laryngoscopy and tracheoscopy
2. Review of concomitant medications
3. Vital signs to include temperature, pulse, respiratory rate, weight, and blood pressure.
4. Performance status evaluation
5. Determination adverse events
6. Serum pregnancy test for women of reproductive potential
7. Quality of Life Questionnaires will be done every fourth cycle
8. Laboratory studies: CBC with differential, serum chemistries, liver function tests starting on day 1 of Cycle 2
9. Urinalysis and TSH and Free T4 will be done every fourth cycle
10. CT scans of chest and abdomen will be done during cycle 8
11. Correlative blood collection on Day 1 of each Cycle that corresponds to an operating room visit.

After clinically evident progression the patient will be seen for a study visit, at which the following will be addressed:

1. Directed physical examination with flexible fiberoptic laryngoscopy and tracheoscopy
2. Review of concomitant medications
3. Performance status evaluation
4. Determination adverse events
5. Laboratory studies: CBC with differential, serum chemistries, liver function tests, urinalysis, T3, FT4, and TSH

Fresh tumor specimens will be obtained if feasible during therapy if the patient undergoes examination under general anesthesia and/or debridement for a standard-of-care clinical purposes per the study flow chart.

---

*CONFIDENTIAL*

*This document is confidential. Do not disclose or use unless authorized.*

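### The 25% response rule compares one airway score across clinic and operating-room examinations of different described reach, with no stated reference examination and no per-site way to record that a site was not seen

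*Combined protocol and SAP*

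**What the plan says.** Sections 4.2.3.1 and 10.1.2.6.1 define partial response (PR) as a fall of at least 25%, and progression (PD) as a rise of at least 25%, in the summed laryngeal and tracheo-bronchial score. Confirmation must come at least 4 weeks later. The scored sites include the carina and mainstem bronchus. Neither definition says which examination the change is measured from.

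The same score is taken at two kinds of examination:

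- **Operating room.** Before drug, "subjects will undergo a comprehensive laryngoscopy and tracheobronchoscopy to map and score their disease burden" (2.1). On treatment, "a comprehensive laryngoscopy, tracheoscopy, and bronchoscopy will be performed every 4 cycles in the operating room" (9.1, footnote 22).
- **Clinic, every 3 weeks.** Section 2.1 describes a "transnasal flexible laryngoscopy and tracheoscopy examination to assess clinical response on treatment", and 10.1.5.2 a "Directed physical examination with flexible fiberoptic laryngoscopy and tracheoscopy". The scoring sheets are completed at each of these sessions, held "within +/- 24 hours that they receive each dose of pembrolizumab" (10.1.2.3).

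The clinical imaging row of the flow chart (9.1) allows bronchoscopy as an option. No section states how far the clinic examination must reach.

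On the Appendix A sheets the number of affected sites (AS) is a tally of ticked boxes. Surface area (SA) and lumen obstruction (LO) are circled from 0 to 3, where 0 means no involvement or obstruction. There is a visit-level Yes/No box for direct bronchoscopy (sheet page 1) and a region-level box for no papilloma (page 4), but no per-site entry for a site not examined.

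**The concern.** A percentage change in a summed score is interpretable only if both sums cover the same sites. Here the fuller examination comes first and the next ones are described more narrowly. If bronchial or carinal points counted before drug are simply absent from a clinic sheet, the score falls although the disease has not changed. The primary endpoint is best overall response (14.1), so one confirmed PR of this kind would be kept whatever later examinations show.

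With the operating-room examination as reference, the error runs towards PR. If a clinic examination were the reference, a fuller operating-room examination could raise the score, but a clinic examination of the same reach as that reference would not confirm the rise.

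**Working it through.** **1. Which examination is the baseline?** Section 2.1 places the mapping and scoring, and the pre-treatment biopsy, at the comprehensive pre-drug examination. Section 8.1.1 takes tissue at the baseline endoscopy and at each operating-room visit. Sheet page 1 has a Baseline option in its visit field, next to a date of surgery. Together these imply the pre-drug comprehensive examination. Footnote 21 of 9.1 gives only timing: "Endoscopic evaluations at baseline should be done within 6 weeks prior to enrollment into the study". The Rapid Review text in 10.1.2.6 shows that a screening clinic video and an operating-room video both exist. The response definitions refer to neither.

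**2. How large a false fall is possible?** Let S be the baseline total and u the points at sites not viewed later and carried as nothing. With disease unchanged, the apparent fall is u/S. It reaches 25% when S ≤ 4u. From sheet pages 4 and 6:

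| What is lost | u | 25% fall if total is at most |
|---|---|---|
| Bronchus ticks only (right, left) | 1 to 2 | 4 to 8 |
| Ticks plus SA and LO for bronchus | 1+1 = 2, up to 2+3+3 = 8 | 8 to 32 |
| Also SA and LO for carina | up to 2+6+6 = 14 | 56 |

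The sheet maximum is 53 + 29 = 82. The first row needs only that unseen sites stay unticked. The other two also need SA and LO rows left blank and summed as 0, or 0 circled for sites not seen. That is an assumption.

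**3. Can clinic visits alone confirm it?** Clinic examinations at weeks 3, 6 and 9 precede the week-12 operating-room examination. Weeks 3 and 9 are 42 days apart. With ±3-day windows the minimum is 42 − 6 = 36 days. For distant patients, "For patients who have to travel >50 miles for treatment, there will be a window of +/- 7 days for each visit", so the minimum is 42 − 14 = 28 days. If the 24-hour allowance between examination and dose is added at both ends, the minima become 34 and 26 days, and only the last is below 4 weeks. So confirmation without an operating-room examination is ordinarily possible.

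**4. The design's own figures (14.1).** The rule is to continue with at least 2 responses in 11 and to succeed with at least 6 in 21. With X₁ ~ Bin(11, p) and X₂ ~ Bin(10, p):

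- Early stop at p = 0.15: P(X₁ ≤ 1) = 0.492 (plan: 49%).
- Success: Σ over x ≥ 2 of P(X₁ = x)·P(X₂ ≥ 6 − x) = 0.0793 at p = 0.15 (plan: 8%) and 0.857 at p = 0.38 (plan: 86%).

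All three reproduce. The sample size is not in question.

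**5. Illustration only.** Suppose exactly one of the 21 patients is counted as PR regardless of drug effect and the other 20 respond at 15%.

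- In stage 1: Σ over x ≥ 1 of P(Bin(10) = x)·P(Bin(10) ≥ 5 − x) = 0.168.
- In stage 2: Σ over x ≥ 2 of P(Bin(11) = x)·P(Bin(9) ≥ 5 − x) = 0.158.
- Weighted: (11 × 0.1682 + 10 × 0.1582)/21 = 0.163.

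The documents give no misclassification rate, so this shows only how sensitive a 6-of-21 rule is to one patient.

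**6. Site count.** Sections 4.2.3.1 and 10.1.2.6 give 6 tracheo-bronchial subsites and a maximum of 6 + 12 + 12 = 30. The sheet counts 0 to 5, with no carina box, and SA plus LO up to 24, so its maximum is 29. This mismatch does not itself lower a score over time.

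**The case against.** The strongest reply is that the baseline is clear enough in context, and that the rest needs several unproven conditions at once: distal disease at baseline, not viewed in clinic, worth at least 25% of the total, entered as nothing, and not queried. Much of this stands. The baseline is implied, so the gap there is a missing statement rather than a missing examination. No section says that clinic examinations miss the bronchi. An uncircled SA or LO row is blank, not 0, and missing or questionable data are queried (Appendix J, 3.10.1). The tick tally, where an unseen site and a clear site look the same, puts only 1 or 2 points at risk, and the text reports laryngeal scores up to 43 in previous studies. Clinic examinations are video-recorded, so their extent can be checked afterwards. Patients with tracheal or pulmonary involvement also have CT volumetry or RECIST as a further measure. The Appendix G forms and the cited sources for the instrument were not available and may hold a convention for unviewed sites.

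What does not fall away is that none of these safeguards is a scoring rule. Rapid Review covers each site's first three cases, a circled 0 raises no missing-data query, and the response definitions do not say that CT overrides a clinical PR.

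A reader might also infer from 7.1.2 that cross-examination comparison of the PR score is written into the plan, since treatment continues after progression at operative endoscopy "until the next in-office clinical examination in 3 weeks which confirms progressive disease of the target lesion". That sentence concerns progression of a target lesion and continuation of treatment. It mentions neither the summed score nor PR.

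**Conclusion.** The point holds in limited form. The plan compares one summed score across examinations of different described reach, leaves the reference to inference, and has no per-site record of what was seen. In a patient with bronchial or carinal disease at baseline that clinic examinations do not view, unchanged disease could be confirmed as a PR. The tick tally alone does this only at totals up to 4 to 8. Totals up to 32, or 56 with the carina, depend on the data-entry assumption in the working. The number of patients exposed is not in the documents, and the 7.9% to 16.3% shift assumes one certain false PR, so it should not drive the rating. This is a minor-to-moderate correction to the primary endpoint's wording, limited to the protocol text and Appendix A.

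Two further inferences are not supported. One is that larynx-only patients cannot be affected. The bronchial mechanism does not reach them, but the sheet separates direct from indirect laryngoscopy and nothing shows that the two score alike. The other is that the Cycle 1 clinic score would isolate the artefact. Baseline endoscopy may precede enrolment by up to 6 weeks, so real change or the effect of biopsy could also move that score.

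**What to change.** In 10.1.2.6.1, and in the matching text of 4.2.3.1:

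1. Name the pre-drug comprehensive examination as the reference for the 25% change.
2. Compute each change only over sites visualised at both the reference and the current examination. Alternatively, compare within examination type, which also requires a named clinic reference.
3. Add a per-site not-examined entry to the Appendix A sheets, and exclude such sites from both sums. The existing bronchoscopy Yes/No box can support this.
4. Separately, reconcile the tracheo-bronchial site count and maximum between text (6 and 30) and sheet (0 to 5 and 29, no carina box).

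The cost is endpoint wording and a small form edit. No visit is added, and the 11/21 design with its 8% and 86% is unchanged. The downside is that a response based on clinic examinations would not cover bronchial sites that were not visualised, and reports should say so.
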